1.3 SOA	Removal of COVID-19 SARS-CoV-2 testing at Day 57, 113 and CC1 and early withdrawal testing.	IP is only administered once at the beginning of the study, and the remainder of the visits are data collection. Therefore, there is no reason to retest for COVID as withdrawal from the study will not occur based on a positive COVID test alone.
1.3 SOA	Addition of collection of smoking status information	To aid understand impact of smoking on CCL17 levels
1.3 SOA	Update to footnotes	Administration update
1.3 SOA	Extending visit window to \pm 4 days for visits on Day 141, 155 and CC1	To aid with compliance to the study schedule
2.3.1 Risk Assessment	Deletion of 'COVID-19 Contingency Plan Any subject that presents with COVID-19-related symptoms and/or has a positive SARS-CoV-2 PCR will be excluded from (further) participation in the trial and will receive follow-up medical attention as per local procedure'	Contradicts text in 7.2.3 – Covid stopping criteria

4.2 Scientific Rationale for Study Design	Updated protocol reference	Administration change
5.1 Inclusion Criteria #7	Geographical Ancestry criteria for Chinese participants update to include participants from Chinese Hong Kong or Taiwan	To aid with participant recruitment
5.1 Inclusion Criteria Requirements for Male Participants schematic	Removal of 'Requirement for Male Participants' schematic	Included in error. Decision tree is required for internal use only.
6.3 Measures to Minimize Bias: Randomization and Blinding	Removal of '(sponsor-open)' in text of section	This study is double blind and not sponsor-open. This was initially added in error so needed to be removed in this amendment.
7.2.3 SARS-CoV-2 related stopping criteria	Removal of COVID stopping criteria	This criterion is no longer necessary as a positive COVID test alone will not be reason for withdrawal from the study. COVID testing has been removed from the study, except testing prior to Day 1.

TABLE OF CONTENTS

	PAGE
TITLE PAGE	1
PROTOCOL AMENDMENT SUMMARY OF CHANGES TABLE	2
TABLE OF CONTENTS	5
1. PROTOCOL SUMMARY	8
1.1. Synopsis	8
1.2. Schema	12
1.3. Schedule of Activities (SoA).....	13
2. INTRODUCTION.....	18
2.1. Study Rationale	18
2.2. Background	18
2.3. Benefit/Risk Assessment	19
2.3.1. Risk Assessment	20
2.3.2. Benefit Assessment.....	28
2.3.3. Overall Benefit: Risk Conclusion	28
3. OBJECTIVES AND ENDPOINTS	29
4. STUDY DESIGN	31
4.1. Overall Design	31
4.2. Scientific Rationale for Study Design	31
4.3. CC1	33

1. PROTOCOL SUMMARY

1.1. Synopsis

Protocol Title:

A Randomised, Double-blind, Placebo-controlled Study of the Safety, Tolerability, Pharmacokinetics, Target Engagement and Immunogenicity of a single subcutaneous dose of GSK3858279 administered to Healthy Caucasian, Chinese and Japanese Participants

Brief Title:

Safety, tolerability, pharmacokinetics and target engagement of GSK3858279 after a single subcutaneous dose in healthy Caucasian, Chinese and Japanese participants.

Rationale:

The purpose of this study is to evaluate the safety, tolerability, pharmacokinetics (PK), target engagement (TE) and immunogenicity of a single subcutaneous (SC) dose of GSK3858279 when administered to healthy Caucasian, Chinese and Japanese participants.

This study will facilitate inter-ethnic comparisons while minimising variations rendered by cross-study assessments.

The outcomes of this study are intended to support the inclusion of Chinese and Japanese participants in global Ph2/3 studies.

Objectives and Endpoints

Objectives	Endpoints
• Primary	

 To evaluate the safety and tolerability of a single SC dose of GSK3858279 compared with placebo administered to healthy participants including cohorts of Japanese, Chinese and Caucasians 	
 Incidence of adverse events (AEs), serious adverse events (SAEs), withdrawals due to AEs Occurrence of clinically important changes from baseline in clinical laboratory parameters (haematology, clinical chemistry, urinalysis), vital signs (blood pressure, heart rate, body temperature), and cardiac parameters (electrocardiogram)

 To assess the pharmacokinetic (serum PK) profile up to 56 days following a single SC dose of GSK3858279 in 	
 PK parameters: area under the concentration-time curve (AUC(0-56), AUC(0-t) post-dose), time of

Objectives	Endpoints
healthy participants including cohorts of Japanese, Chinese and Caucasians	occurrence of last quantifiable concentration (tlast), maximum observed concentration (Cmax), and time of occurrence of Cmax (tmax) per cohort as data permits

 • Secondary 	

 • To evaluate target engagement (TE) up to 56 days following a single SC dose of GSK3858279 in healthy participants including cohorts of Japanese, Chinese and Caucasians. 	
 • Reduction (%) from baseline in free CCL17: maximum, minimum and at Days 7, 14, 28 and 56, post-dose • Total CCL17 (free and when bound to GSK3858279): maximum observed concentration (Cmax), time of Cmax (tmax), maximum fold increase compared to baseline, fold increase compared to baseline at Days 7, 14, 28 and 56, post-dose.

 • To assess the potential for anti-drug antibody (ADA) formation 	
 • Incidence of pre-existing ADAs • Incidence of treatment-emergent ADAs over time (and whether neutralising)

 • Exploratory 	
CCI	

Objectives	Endpoints
CCI	

Overall Design:

This is a randomised, double-blind, placebo-controlled, study with a single SC dose of GSK3858279 administered to healthy Caucasian, Chinese and Japanese participants.

To try to eliminate any time dependant variability among ethnic groups, we will aim to treat Caucasian and Asian groups concurrently.

Participants will attend a screening visit at the clinical units within 28 days of Study Day 1. If eligible for the study, participants will return on Day -1 and maybe admitted to the unit overnight for final screening checks in preparation for randomization and dosing (Day 1). Participants will remain at the clinical units until Day 3.

- All participants will remain in the study until at least CCI. It will be mandatory for the Caucasian cohort to continue CCI. The extended follow-up period CCI is to better understand the apparent non complete return of free CCL17 to baseline values as observed in Part A of Study 207804 across all dose groups. CCI (primary endpoints defined from data up to and including Day 57). Safety information will be collected throughout the study.
- Study intervention will be administered as four separate SC injections of either GSK3858279 CCI or placebo in a 7:3 ratio, respectively for each cohort.

Study Population

Although reproductive toxicity studies have not yet been conducted, both males and females (of non-reproductive potential) are permitted under the conditions specified (see Inclusion Criteria).

Healthy participants have been chosen because:

- Comorbidities and concomitant medications of patient participants may confound analysis.
- Patient participants (e.g. osteoarthritis) will derive little or no benefit from a single dose of GSK3858279, and their participation in this study would preclude treatment with accessible efficacious therapies.

Number of Participants:

Approximately 10 participants are to be randomized (7 active: 3 placebo) per cohort aiming to achieve at least 6 evaluable participants on active and 2 on placebo per cohort. An evaluable participant is one that has been dosed and has safety and all PK data up to Day 57.

Replacements (assigned to the same treatment) are permitted at the discretion of the sponsor in consultation with the investigator. For example, in the event of a participant withdrawing before Day 57 the participant will be replaced.

Note: Enrolled means a participant's, or their legally acceptable representative's, agreement to participate in a clinical study following completion of the informed consent process and screening. Potential participants who are screened for the purpose of determining eligibility for the study, but do not participate in the study, are not considered enrolled, unless otherwise specified by the protocol. A participant will be considered enrolled if the informed consent is not withdrawn prior to participating in any study activity after screening.

Intervention Groups and Duration:

Three cohorts of approximately 10 participants in each cohort (Caucasian, Chinese and Japanese) will be randomized to a single dose of **cci** SC GSK3858279 or placebo (7:3 ratio) ([Appendix 1](#)).

- Approximately 10 eligible participants per cohort will be admitted to the clinical unit on the day prior to dosing (Day-1). On Day 1, each participant will receive a SC dose of GSK3858279 or placebo, administered as four separate SC injections, in a 7:3 ratio, respectively.
- Participants will then remain as an in-patient until discharged on Day 3 after assessments have been performed.
- Participants will then return to the clinical unit for outpatient visits as described in the SoA.

[figure not shown]
- The final required follow up visit will be at the clinical unit on **CCI** for Chinese and Japanese participants. NB: Japanese and Chinese participants have an option to remain in the study **CCI**.
- The final follow up visit will be at the clinical unit on **CCI** for Caucasian participants.
- The maximum dose will not exceed **CCI** SC.

The study duration is not expected to exceed a maximum of **CCI**: (Screening [up to 28 days] and a follow-up period of up to **CCI**. Follow-up may be extended if a serious or clinically significant AE has not resolved by **CCI**.

Data Monitoring/ Other Committee:

No blinded Safety Review Team (uSRT)

CCI

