6.3. Measures to Minimize Bias: Randomization and Blinding

Participants who meet the screening eligibility criteria will be randomised to a treatment group through the Interactive Web Response System (IWRS). Before the study is initiated, the log in information and directions for the IWRS will be provided to the site.

Once assigned, a randomisation number must not be reassigned to another participant in the study. This will be a double blind study with both the investigator and participant blinded to study treatment. Site personnel will remain blinded. There will, however, be an unblinded site pharmacy personnel to prepare the study intervention; but they will not have contact with study participants

The following will apply:

- The IWRS will be programmed with blind-breaking instructions. In case of an emergency, the investigator has the sole responsibility for determining if unblinding of a participants' intervention assignment is warranted. Participant safety must always be the first consideration in making such a determination.
- If the investigator decides that unblinding is warranted, the investigator should make every effort to contact GSK prior to unblinding a participant's intervention assignment unless this could delay emergency intervention of the participant. If a participant's intervention assignment is unblinded, GSK must be notified within 24 hours after breaking the blind.
- The date and reason that the blind was broken must be recorded in the source documentation and case report form, as applicable.
- GSK's Safety and Medical Governance (SMG) staff may unblind the intervention assignment for any participant with an SAE. If the SAE requires that an expedited regulatory report be sent to one or more regulatory agencies, a copy of the report, identifying the participant's intervention assignment, may be sent to investigators in accordance with local regulations and/or GSK policy.
- Sites will be required to make every effort to ensure that the results of study laboratory tests are not proactively communicated to participants during the study unless essential for clinical care.

GSK3858279 PK and Free and Total CCL17 results that may unblind the study will not be reported to investigative sites or blinded personnel until the study has been unblinded.

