A participant will be withdrawn if the participant's intervention code is unblinded by the investigator or treating physician. The primary reason for discontinuation (the event or condition which led to the unblinding) will be recorded in the CRF. The participant will be followed up for safety monitoring if treatment was received

GSK's Safety Evaluation and Risk Management (SERM) staff may unblind the intervention assignment for any participant with an SAE. If the SAE requires that an expedited regulatory report be sent to one or more regulatory agencies, a copy of the report, identifying the participant's intervention assignment, may be sent to investigators in accordance with local regulations and/or GSK policy.

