4. STATISTICAL ANALYSES

4.1. General Considerations

4.1.1. General Methodology

Participants who withdraw from the study may be replaced, with any replacements beginning from the start of the study.

Summary tables will provide the following descriptive statistics as a minimum, unless otherwise specified:

- Continuous data (normally distributed):
n, mean, standard deviation (SD), median, minimum and maximum.
- Continuous data (log-normally distributed):
n, geometric mean, SD on the log scale (SD (log)), median, minimum and maximum.
- Categorical data:
number and percentage of participants in each category.

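### If the investigator breaks a code before Day 57, same-treatment replacement can show that investigator the replacement's arm before dosing

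*Protocol*

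**What the plan says.** Four rules bear on this point.

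- **Blinding.** Protocol 6.3: "This will be a double blind study with both the investigator and participant blinded to study treatment". In an emergency, "the investigator has the sole responsibility for determining if unblinding of a participants' intervention assignment is warranted".
- **Code break.** Protocol 6.3: "A participant will be withdrawn if the participant's intervention code is unblinded by the investigator or treating physician". If treatment was received, safety follow-up continues.
- **Replacement, protocol.** Synopsis 1.1, repeated in Protocol 9.3 and SAP 5: "Replacements (assigned to the same treatment) are permitted at the discretion of the sponsor in consultation with the investigator". The synopsis then adds as an example: "in the event of a participant withdrawing before Day 57 the participant will be replaced".
- **Replacement, SAP.** SAP 4.1.1: "Participants who withdraw from the study may be replaced, with any replacements beginning from the start of the study". A replacement is therefore newly screened and dosed.

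Each cohort randomises about 10 participants, 7 to active and 3 to placebo, to secure 6 and 2 evaluable. Evaluable means dosed, with safety data and all PK data up to Day 57 (Protocol 1.1 and 9.3; SAP 5).

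**The concern.** Each rule is unremarkable alone. Together they let information about one participant's arm carry over to another. The investigator who breaks a code normally learns the arm, and is then consulted on a replacement who must receive that same arm. No section excepts code-break withdrawals, conceals whom a new participant replaces, or calls for a different site or assessor.

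Two things are exposed for that one replacement:

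- **Selection.** Several eligibility decisions rest on investigator judgement (for example Protocol 5.1 criterion 1 and 5.2 criteria 3, 17 and 30), and clinical status is re-checked before dosing on Day 1. These would be made with the arm known.
- **Adverse events.** The investigator decides whether a finding is recorded as an AE, and assigns its intensity and causality (Protocol 10.3.1 and 10.3.3). The related-AE and related-SAE tables use that causality call (SAP 4.5.1). One study-halt criterion in Protocol 7.2 also turns on the investigator's view of whether an abnormality may relate to the product.

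The safety objective is a comparison with placebo in very small groups, and SAP 4.7.1 plans to give regulators individual as well as aggregate data. One participant assessed with the arm known is therefore visible.

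**Working it through.** The plan gives no figure to reproduce on this point. The check is a reading of the rules in sequence, with simple arithmetic for size.

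**Does the chain hold?**

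1. The investigator breaks a code before Day 57. Protocol 6.3 withdraws the participant.
2. Protocol 6.3 provides for continued safety follow-up but not for PK sampling, so the participant will probably not meet the evaluable definition.
3. The synopsis example says that such a participant is replaced. Protocol 9.3 and SAP 5 only permit it, and SAP 4.1.1 says it may happen. The strength of the rule differs by section; a code break is excepted in none of them.
4. The replacement takes the same arm, after consultation with the investigator.
5. The other safeguards do not break the link. A randomisation number cannot be reassigned (Protocol 6.3), but the replacement simply has a new number on the same arm. PK and CCL17 results are withheld from sites (Protocol 6.3, 8 and 8.4) and site codes are released only after full analysis (Protocol 10.1.7). These close other routes.

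The chain holds on the text, subject to two conditions: the investigator saw the code, and knows which enrolment is the replacement.

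**What does the investigator gain?** From the 7:3 ratio alone, the best guess (always active) is right 7/10 = 70% of the time. For a replacement known to match a revealed arm it is right 100% of the time.

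**How much of the safety data is affected?** The Safety set keeps everyone who received at least one injection (Protocol 9.2; SAP 3). If the withdrawn participant was dosed, both that person and the replacement are in it:

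| Arm | Randomised | With replacement | Share with known arm |
|---|---|---|---|
| Active | 7 | 7 + 1 = 8 | 1/8 = 12.5% |
| Placebo | 3 | 3 + 1 = 4 | 1/4 = 25% |

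**Is the replacement needed?** One loss leaves 7 − 1 = 6 active or 3 − 1 = 2 placebo, exactly the stated minimum. The first loss in an arm need not be replaced, provided nobody else in that arm becomes non-evaluable.

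The documents give no code-break rate, so no frequency is computed.

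**The case against.** The best case against the point is that it concerns a rare event at the edge of a descriptive study. Emergency unblinding of healthy participants after a single dose should be uncommon. Replacement is the sponsor's choice, assignment runs through the IWRS, and the study is multi-centre (Protocol 4.1), so the replacement could enter elsewhere. A treating physician could be the one who breaks the code. No section says that the site is told which enrolment is the replacement. No hypothesis is tested. All of this stands, and it limits how often the problem arises. It does not supply a rule that prevents it, and consulting the investigator makes knowledge of the link plausible.

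A reader might infer more than the documents support:

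- *That the double blind fails outright.* Only the investigator's blind is at risk. The replacement need not learn the arm.
- *That investigator judgement of laboratory and ECG changes makes up the co-primary safety endpoint.* SAP 4.5.2 and 6.2.1 tabulate laboratory, vital-sign and ECG changes mostly against numeric limits. Judgement enters when a finding is recorded as an AE (Protocol 8.2.4 and 10.3.1). The primary AE endpoint is incidence; intensity and causality appear in supporting summaries.
- *That replacement follows straight after a serious reaction.* Protocol 7.2 temporarily halts the study after any SAE reasonably attributed to the product, and recruitment resumes only after review and approvals. A halt does not restore the blind, but it contradicts that picture.
- *That expedited reports create the same exposure.* Protocol 6.3 does allow that "a copy of the report, identifying the participant's intervention assignment, may be sent to investigators in accordance with local regulations and/or GSK policy", but such a report does not itself trigger withdrawal. A separate withdrawal before Day 57 would be needed.
- *That the shares are 1 of 7 and 1 of 3.* For safety data, those denominators omit a dosed participant who stays in the Safety set.

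**Conclusion.** The point holds in a limited form. The stated rules, followed as written, can tell an investigator the arm of a newly enrolled participant before dosing, which works against the blinding in Protocol 6.3. The size is one participant per event: 1 of 8 active or 1 of 4 placebo in a cohort's Safety set. The exposure is mainly in selection and in AE reporting, intensity and causality. PK and target-engagement values come from assays and are little affected, so the ethnic comparisons of AUC(0-56) and Cmax are not in question.

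This assumes that the code is broken before Day 57, that the investigator saw it and knows whom the new participant replaces, that the sponsor chooses to replace, and that the withdrawn participant had been dosed. It is a cheap improvement best made before any code break, not a flaw that threatens the study's conclusions.

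**What to change.** Leave the withdrawal rule alone and change the replacement rule in Protocol 1.1 and 9.3 and SAP 4.1.1 and 5:

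1. Use one verb. Reconcile *will be* (synopsis example), *permitted* (1.1, 9.3, SAP 5) and *may be* (SAP 4.1.1).
2. State that a participant whose assignment is known to the site is not replaced while the cohort can still reach 6 evaluable on active and 2 on placebo.
3. If a replacement is needed to reach that minimum, the IWRS and named unblinded sponsor staff make and hold the link. The site is told neither which enrolment is the replacement nor whom it replaces.
4. Flag in the safety listings any replacement whose arm the site could have inferred. Concealing the link may not suffice where an enrolment beyond the planned number gives itself away.

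**Cost.** Wording and an IWRS setting, plus naming who holds the link, since Protocol 6.3 assigns no sponsor role for it. The affected arm may end with 6 rather than 7 evaluable on active, or 2 rather than 3 on placebo, which is still the stated minimum.

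Drawing the replacement from a fresh randomised 7:3 block would conceal the arm but might not refill the depleted one. A missing placebo participant would be supplied by the first draw only 3/10 = 30% of the time. The expected number of draws to the first placebo is (10 + 1)/(3 + 1) = 2.75, and at worst 8. That could dose extra healthy volunteers for no gain, so it is not recommended.

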1.3. Schedule of Activities (SoA)

Screening period

Procedure	Screening (Day -28 to Day -1)
Informed consent	X
Inclusion and exclusion criteria	X
Demography	X
Full Physical examination including height and weight	X
Medical/medication/drug/alcohol history ¹	X
Alcohol & Tobacco screens ²	X
Urine drug screen	X
FSH (in WONCBP)	X
HIV, Hepatitis B and C screening	X
Haematology, clinical chemistry, urinalysis	X
COVID-19 (SARS-CoV-2) PCR or rapid antigen test	X
TB screening (QuantiFERON)	X
12-lead ECG ³	X
Vital signs ⁴	X
Echocardiogram	X
AE assessment	X
SAE assessment	X
Target Engagement Sample Collection	X

1. To include substance usage, family history of premature cardiovascular disease, medication, drug/alcohol history
2. As per local standard practice
3. Performed in triplicate
4. Vital signs are to be taken before blood collection for laboratory tests

Treatment and Follow-up

Procedure	Treatment and Follow-up (FU)																	
	1	2	3	4	CCI	EW ¹												
Week																		
Day	-2	-1	1 ^a	2 ^a	3 ^a	5 ^b	8 ^b	15 ^b	22 ^b	29 ^b								
Outpatient visit	X					X	X	X	X	X	X	X	X	X	X	X	X	X
Inpatient Stay		X	X	X														
Discharge from clinical unit					X													
Inclusion and exclusion criteria			X ²															
Brief Physical examination			X ³	X				X									X	X
Alcohol & Tobacco screens		X																
Urine drug screen		X																
12-lead ECG (triplicate)		X	X ⁴	X	X		X	X	X	X	X	X	X	X	X	X	X	X
Vital signs		X	X ⁵	X	X		X	X	X	X	X	X	X	X	X	X	X	X
Smoking Status		X				X	X	X	X	X	X	X	X	X	X	X	X	X

Procedure	Treatment and Follow-up (FU)															
	Week						1	2	3	4	CCI	EW ¹				
Day	-2	-1	1 ^a	2 ^a	3 ^a	5 ^b	8 ^b	15 ^b	22 ^b	29 ^b						
Haematology, clinical chemistry, urinalysis		X	X	X	X		X	X	X	X	X	X ⁶	X	X	X	X
COVID-19 SARS- CoV-2 PCR or rapid antigen test	X ⁷															
Randomization			X													
Dosing (SC) injections			X ⁸													
PK & TE	X ⁹		X ¹⁰	X ¹⁰	X ¹⁰	X	X	X	X	X	X	X	X	X	X	X
Immunogenicity			X ¹¹					X		X		X		X		X
PD serum/plasma samples (For protein biomarkers)			X		X		X	X	X	X						X
PD WB PAXgene samples (For transcriptomic analyses)			X		X		X		X							X

Procedure	Treatment and Follow-up (FU)										
	1	2	3	4	CC1	EW ¹					
Week											
Day	-2	-1	1 ^a	2 ^a	3 ^a	5 ^b	8 ^b	15 ^b	22 ^b	29 ^b	
PGx			X ¹²								
SAE and AE (SAEs recorded throughout. AEs recorded from first SC injection)	<----->										X
Concomitant meds	<----->										X

AE= adverse event; ECG= Electrocardiogram, SC = subcutaneous; PD = pharmacodynamics, PK= pharmacokinetics; SAE= serious adverse event, TE = Target engagement

* Visits optional for Chinese and Japanese participants

^a ± 2hrs

^b ± 1 day

^c ± 4 day

- 1 Early withdrawal
- 2 Re-check clinical status before dose of study medication
- 3 Prior to dosing
- 4 pre-dose and 60 mins post start of SC injections
- 5 pre-dose, 30 mins, 1h, 2h, 3h & 4 h post start of SC injections
- 6 NT-pro BNP. NB: Troponin I at all time points
- 7 Result to be available prior to dose of study drug. Day -2 for PCR or rapid antigen test
- 8 Study intervention administered as 4 separate injections
- 9 Only TE sample
- 10 PK and TE blood samples taken pre-dose, 6h, 12h, 24h, 36h and 48h post start of SC injections, respectively
- 11 Blood sample to be taken pre-dose
- 12 Taken pre-dose

- The timing of planned study assessments may change during the course of the study based on emerging data/in-stream data review (e.g., to obtain data closer to the time of peak plasma concentrations) to ensure appropriate monitoring.
- Any changes in the timing of time points for any planned study assessments as the result of emerging pharmacokinetic/pharmacodynamic data from this study must be documented and approved by the relevant study team member and then archived in the sponsor and site study files but will not constitute a protocol amendment.
- The Competent Authority (CA) and ethics committee (EC) will be informed of any safety issues that constitute a substantial amendment and require alteration of the safety monitoring scheme or amendment of the informed consent form (ICF). The changes will be approved by the CA and the EC before implementation.

